5.1 Inclusion criteria

Participants eligible for inclusion in this study must meet all of the following criteria:

- 1. Males and females ≥18 years of age
- 2. Recent ACS (in-patient/out-patient) within 5 weeks of screening, defined as: Ischemic symptoms with unstable pattern, occurring at rest or minimal exertion within 24 hours of an unscheduled hospital admission or emergency department visit, due to presumed or proven obstructive coronary disease AND at least one of the following:
 - a. Elevated cardiac biomarkers (cardiac troponin (cTn) or the MB fraction of creatinine kinase (CKMB)) with at least one value above the 99th percentile of the upper reference limit (URL) or defined by the local laboratory MI diagnosis cut-off values OR
 - b. Resting ECG changes consistent with ischemia or infarction AND additional evidence of obstructive coronary disease
- 3. Serum LDL-C \geq 70 mg/dL or non-HDL-C \geq 100 mg/dL
- 4. Fasting triglycerides <4.52 mmol/L (<400 mg/dL) at screening
- 5. Calculated glomerular filtration rate >20 mL/min by estimated glomerular filtration rate (eGFR)
- 6. Participants must be willing and able to give informed consent before initiation of any study related procedures and willing to comply with all required study procedures
- 7. Participants are required to be on statin therapy, or have documented statin intolerance, as determined by the investigator, following hospitalization (in-patient/outpatient) for an ACS. Statin intolerant patients are eligible if they had intolerable side effects on at least 2 different statins, including one at the lowest standard dose.

5.2 **Exclusion criteria**

Participants meeting any of the following criteria are not eligible for inclusion in this study.

- 1. Any uncontrolled or serious disease, or any medical or surgical condition, that may either interfere with participation in the clinical study, and/or put the participant at significant risk (according to investigator's [or delegate] judgment) if he/she participates in the clinical study.
- 2. An underlying known disease, or surgical, physical, or medical condition that, in the opinion of the investigator (or delegate) might interfere with interpretation of the clinical study results.
- 3. New York Heart Association (NYHA) class IIIb or IV heart failure or last known left ventricular ejection fraction <25%.

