2.2.1 Subgroup of interest

Subgroup analyses of the two primary efficacy variables and the secondary endpoint of absolute change from baseline in LDL-C will be performed for the following subgroups (note that results for a subgroup category will only be presented if the total across both treatment groups within the category is at least 10 participants):

- Background lipid-lowering therapy at baseline: Yes, No
- Medical history of statin intolerance: Yes, No (from medical history statin intolerance CRF page)
- Baseline statin intensity: High, Moderate or Low, None
- Age: <65 years, >= 65 years
- Sex: Male, Female
- Race subgroup 1: White, Non-White/Multiple (unknown will be excluded from subgroup analyses)
- Race subgroup 2: White, Black or African American, Non-White/Non-Black or African American/Multiple (unknown will be excluded from subgroup analyses)
- Ethnicity: Hispanic or Latino, Not Hispanic or Latino (unknown or not reported will be excluded from subgroup analyses)
- BMI: >=30 vs < 30, and >=25 vs < 25 kg/m²
- Renal impairment by eGFR categories at baseline: <15, ≥15 to <30, ≥30 to <60, ≥60 to <90, or ≥90 mL/min/1.73m²
- Baseline LDL-C: <=100 and > 100 mg/dL; by median; and then by quartiles
- Index myocardial infarction: ST segment elevation myocardial infarction (STEMI), Non-ST-segment elevation myocardial infarction (NSTEMI), No myocardial infarction (from ACS medical history)
- Atrial fibrillation associated with index myocardial infarction: Yes, No (from ACS medical history)
- Revascularization procedure during index ACS event: Yes, No (from ACS medical history)
- History of diabetes: Yes, No (from ACS medical history)
- Baseline glycemic status: Diabetes, Pre-diabetes, Normoglycemia

For definition of baseline glycemic status, refer to Section [2.7.3, Table 2-4](#).

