intensity level to post-baseline lipid-lowering therapy addition group, and a shift table for statin intensity from baseline to Day 330/Last Visit will also be provided. To this end, the LLTs and statin intensity for Day 330/Last Visit will be assessed on the Day 330 visit date for participants with recorded Day 330 visit date, or on the study end date (date of last participation) otherwise. For the shift table for statin intensity from baseline to Day 330/Last Visit, the “None” category includes participants who did not take statin post baseline or who stopped the statin during the study.

Changes in LLTs prior to baseline will focus on statin and bempedoic acid taken within 30 days prior to study treatment start date, i.e. any time from day -30 to day -1. Number and percentage of participants will be presented for the following statin categories: initiation of statin therapy (no statin record present at day -30), discontinuation of statin therapy (no statin record present at day -1), increase in statin intensity, decrease in statin intensity, and change of statin within the same intensity group. Treatment gaps and/or overlapping treatment periods in case of two or more statins within the 30-day period will be ignored for analysis. If at least one statin record is present indicating that the statin was taken consistently on all days within the 30-day period, the participant will not be considered as having had any change in statin therapy.

For the analysis of lipid-lowering therapies at baseline a modified lipid-lowering therapy definition is also employed. For this analysis a modified lipid lowering therapy includes any statin, ezetimibe, PCSK9 inhibiting monoclonal antibodies, or bempedoic acid therapies.

The following medications will be included in the lipid-lowering therapy tables.

Table 2-3 Lipid-lowering Therapies

Medication	Medications included
Lipid Lowering Therapy	ATCCODE2=C10
Statin	ATCCODE2=C10 and CMDECOD contains ‘statin’, or ATCCODE4=C10AA, C10BA, or C10BX
Ezetimibe	ATCCODE2=C10 and CMDECOD contains ‘ezetimibe’
PCSK9 inhibiting monoclonal antibodies	ATCCODE2=C10 and CMDECOD contains ‘evolocumab’ or ‘alirocumab’
Bempedoic acid	ATCCODE2=C10 and CMDECOD contains ‘bempedoic acid’
Modified lipid lowering therapy	ATCCODE2=C10 and CMDECOD contains ‘statin’, ‘ezetimibe’, ‘evolocumab’, ‘alirocumab’, or ‘bempedoic acid’

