If a participant is considered a study completer and has a non-missing visit date for the nominal Day 330 visit recorded, a statin assessment date (to assess if the participant was taking statins at this point in time) will be calculated by subtracting 30 days from the Day 330 visit date (e.g., study Day 300 if the participant completes on study Day 330). The statin assessment date will be compared to the maximum statin end date of all statin medications taken by the participant. If the last statin is recorded as ongoing at study end date, the maximum statin end date will be set to the study end date.

If the participant was on a statin on or after this statin assessment day (maximum statin end date \geq statin assessment date), the participant will be considered as discontinued statin = 'no'.

If the participant was not on a statin on and after this statin assessment day (maximum statin end date $<$ statin assessment date), or they were a completer who did not have a Day 330 visit, the participant will be considered as discontinued statin = 'yes'.

All early termination participants will be considered to not be on a statin for this endpoint (the participant will be considered as discontinued statin = 'yes').

Participants who were not taking any statin while on study will be considered to not be on a statin for this endpoint (the participant will be considered as discontinued statin = 'yes').

The analysis will be based on the FAS excluding participants who had medical history of statin intolerance.

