2.6.2 Statistical hypothesis, model, and method of analysis

Analyses of secondary efficacy variables 1 and 7 - 20 will be similar to the primary analysis of primary efficacy variable 1 (using MMRM, but with a two-sided 95% confidence interval for the treatment difference).

Secondary efficacy variables 2, 3, and 22 will be analyzed using an analysis of covariance (ANCOVA) linear model with treatment and baseline LDL-C as explanatory variables. Least-squares mean of each treatment group, 95% confidence interval for the treatment group least-squares means, least-squares mean treatment difference, 95% confidence interval for the treatment difference, and p-value based on the fitted model will be reported. Variables 2 and 3 are calculated by averaging the observed post-baseline values (change or percent change) for each participant across analysis visits Day 90, Day 270, and Day 330. The outcome value for variable 22 is a proportion that is calculated for each participant with total number of study days equal to duration on study as defined in Section 2.3.1.

Secondary efficacy variables 4 - 6 and 23 will be analyzed at each applicable post-baseline visit using a logistic regression model with treatment and baseline LDL-C as explanatory variables (Stokes et al. 2012). The odds ratio, 95% confidence interval for the odds ratio, and p-value based on the fitted model will be reported. Confidence intervals for the percentages per treatment group will be presented and will be derived from the normal approximation to the

binomial distribution. Missing data will be imputed using “non-responder” (i.e., “negative” outcome) imputation.

Secondary efficacy variable 21 will be analyzed at each post-baseline visit using a proportional odds model with treatment and baseline LDL-C as explanatory variables (Stokes et al. 2012). The odds ratios, 95% confidence intervals for the odds ratios, and p-values based on the fitted model will be reported. Confidence intervals for the percentages per treatment group will be presented and will be derived from the normal approximation to the binomial distribution. Missing data will not be imputed.

Analyses of secondary efficacy variables will be based on the FAS.

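### Statin discontinuation (SAP variable 23) selects its analysis set by history of statin intolerance, not by statin use at baseline, so it can count stops that preceded Day 1 and leave out stops that came later

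*SAP*

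**What the plan says.** SAP 2.6.1 defines the analysis set for variable 23 in one sentence: "The analysis will be based on the FAS excluding participants who had medical history of statin intolerance". No sentence asks whether the participant was taking a statin at baseline.

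The coding rules in the same section are:
- For completers with a Day 330 visit, a reference date is set 30 days before that visit. "The statin assessment date will be compared to the maximum statin end date of all statin medications taken by the participant". A last end date before the reference date gives *yes*. There is no lower limit at Day 1.
- "Participants who were not taking any statin while on study will be considered to not be on a statin for this endpoint", which also gives *yes*.
- "All early termination participants will be considered to not be on a statin for this endpoint", again *yes*.

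For the secondary variables in general, SAP 2.6.2 states: "Analyses of secondary efficacy variables will be based on the FAS". Protocol 12.5.1 says the same. SAP Section 4, which lists changes from the protocol, does not mention the intolerance exclusion.

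On who may enter, Protocol 5.1 says: "Participants are required to be on statin therapy, or have documented statin intolerance, as determined by the investigator, following hospitalization". The intolerance criterion there is side effects on at least two statins; it does not require that the person now takes none. SAP 2.2.1 lists intolerance history as one subgroup variable and, separately, "Baseline statin intensity: High, Moderate or Low, None".

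**The concern.** Only someone who is taking a statin can discontinue it. The natural at-risk set is therefore participants on a statin at baseline. History of intolerance is a different variable and a poor stand-in for current use, and it can fail in both directions: it keeps non-users who have no intolerance record, and it drops users who have one.

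At stake is what the endpoint measures. Protocol 4.1 gives the effect of inclisiran on statin discontinuation as its example of why the trial is open label, and names a meaningful difference in statin discontinuations among the reasons for one year of follow-up. Events that happened before Day 1 cannot inform that question. Adding them to both arms raises both rates and pulls the odds ratio toward 1.

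**Working it through.** The plan states no expected rate or power for variable 23 (Protocol 12.8.2 is marked not applicable), so there is no figure to reproduce. The check has two parts.

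**1. The rules applied to individual histories**

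| History | Variable 23 as written | On a statin at Day 1? |
|---|---|---|
| No intolerance record, statin stopped Day -5, none on study | *yes* (by the no-statin rule and by the date rule) | No |
| Intolerance history, on a statin throughout | excluded | Yes |
| Intolerance history, on a statin at baseline, stopped Day 120 | excluded | Yes; a true on-study stop is lost |
| No intolerance record, no statin at baseline, started Day 60 and ongoing | *no* | No |

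The first participant has baseline statin intensity None and stays at None. The variable 21 grid, also in SAP 2.6.1, labels that *No change*. The two variables therefore describe one person in opposite ways.

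**2. Size**

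The documents give neither the number off statin at Day 1 nor the number of intolerant participants on a statin, so what follows is illustration.

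A plausible share off statin: Protocol 4.1 cites one-third stopping over three years. At constant hazard, the share stopping in a 30-day screening period is 1 − (2/3)^(30/1095) = 0.011. In an arm of 192 that is 192 × 0.011 ≈ 2 participants. The hazard soon after starting may be higher, so 2%, 5% and 8% are shown as well.

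Let q be the share of the analysed set off statin at Day 1 and staying off, d the share terminating early, and p the true on-study discontinuation rate among baseline users. The rate coded *yes* is

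q + (1 − q) × [d + (1 − d) × p].

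Assume p = 0.06 with inclisiran and 0.12 with usual care. The true odds ratio is (0.06/0.94)/(0.12/0.88) = 0.47. For d, use 0 and then 0.20, the loss to follow-up assumed in Protocol 12.8.1, taken as a proxy for early termination.

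| q | d = 0: rates | odds ratio | d = 0.20: rates | odds ratio |
|---|---|---|---|---|
| 0 | 0.060 vs 0.120 | 0.47 | 0.248 vs 0.296 | 0.78 |
| 0.011 | 0.070 vs 0.130 | 0.51 | 0.256 vs 0.304 | 0.79 |
| 0.02 | 0.079 vs 0.138 | 0.54 | 0.263 vs 0.310 | 0.79 |
| 0.05 | 0.107 vs 0.164 | 0.61 | 0.286 vs 0.331 | 0.81 |
| 0.08 | 0.135 vs 0.190 | 0.66 | 0.308 vs 0.352 | 0.82 |

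Example for q = 0.05 and d = 0: 0.05 + 0.95 × 0.06 = 0.107 and 0.05 + 0.95 × 0.12 = 0.164; the odds are 0.1198 and 0.1962, ratio 0.61.

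Users excluded: if 5% to 20% of 384 have an intolerance history and 10% to 50% of those take a statin, between 384 × 0.05 × 0.10 ≈ 2 and 384 × 0.20 × 0.50 ≈ 38 participants are removed. Both ranges are assumptions.

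**The case against.** The protocol defines the variable as a state of non-use over the last 30 days, with no baseline condition, and a participant off statin throughout meets that definition. This is fair as a reading of the protocol. It does not rescue the SAP, which already restricts the population and does so on the wrong variable.

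Other planned analyses will show part of the picture. Variable 21 compares each visit with baseline statin intensity and has no intolerance exclusion, and SAP 2.4.2 plans a shift table of statin intensity to Day 330/Last Visit. This stands, but variable 21 pools stopping with any fall in intensity, and the shift table makes no comparison between arms.

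The shares off statin are unsupported. This stands too. Eligibility requires a statin or documented intolerance, Protocol 4.1.1 ties that to identification and screening with no planned change in therapy, and screening lasts at most 30 days. The category in SAP 2.4.2 for statins stopped by the day before Day 1 shows that the case is provided for; a reader might infer that such participants are expected in number, and a table category does not show that.

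This is also the last of 23 secondary variables and has no power basis, which limits the consequence.

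A reader might infer that the rule favours one arm. The documents do not support this: statin status at Day 1 and intolerance history both precede randomization, so in expectation they fall equally in the two arms.

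**Conclusion.** The analysis set for variable 23 is wrongly defined. That follows from the text alone: no baseline-statin condition, an exclusion on a separate variable, a contradiction with variable 21, and an undeclared departure from the FAS stated in SAP 2.6.2 and Protocol 12.5.1.

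The numerical effect is uncertain and probably modest. It is mislabelling and dilution toward an odds ratio of 1. With no early termination, the assumed 0.47 becomes about 0.51 at the share implied by the protocol's cited rate, and 0.54 to 0.66 if 2% to 8% are off statin. With 20% early termination coded *yes* in both arms, most of the dilution has already happened (0.78), and this issue adds little (0.79 to 0.82). It would be wrong to conclude that correcting the set alone recovers the true effect; the coding of early terminators is a separate matter.

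Nor do the documents show that statin users have in fact been excluded. The definitions allow it; no count is given. All rates and shares in the illustration, apart from the cited one-third over three years and the planned 20% loss, are assumptions.

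**What to change.** In SAP 2.6.1, replace the last sentence for variable 23 with: *The analysis will be based on FAS participants taking a statin at baseline, defined as a statin record that starts on or before study Day 1 and is ongoing on or ends on or after Day 1, regardless of history of statin intolerance.* The explicit dates matter, because the general baseline rule (last value before dosing) could otherwise let a statin stopped on Day -5 count as baseline use.

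Then:
- remove the rule that codes participants with no statin on study as *yes*, which becomes redundant;
- make SAP 2.6.2 consistent with this set;
- list the restriction in SAP Section 4 as a change from Protocol 12.5.1;
- describe baseline non-users separately.

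The cost is SAP wording and one filter on medication dates already collected. The analysed number changes slightly, and no new data are needed.

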2.6.2 Statistical hypothesis, model, and method of analysis

Analyses of secondary efficacy variables 1 and 7 - 20 will be similar to the primary analysis of primary efficacy variable 1 (using MMRM, but with a two-sided 95% confidence interval for the treatment difference).

Secondary efficacy variables 2, 3, and 22 will be analyzed using an analysis of covariance (ANCOVA) linear model with treatment and baseline LDL-C as explanatory variables. Least-squares mean of each treatment group, 95% confidence interval for the treatment group least-squares means, least-squares mean treatment difference, 95% confidence interval for the treatment difference, and p-value based on the fitted model will be reported. Variables 2 and 3 are calculated by averaging the observed post-baseline values (change or percent change) for each participant across analysis visits Day 90, Day 270, and Day 330. The outcome value for variable 22 is a proportion that is calculated for each participant with total number of study days equal to duration on study as defined in Section 2.3.1.

Secondary efficacy variables 4 - 6 and 23 will be analyzed at each applicable post-baseline visit using a logistic regression model with treatment and baseline LDL-C as explanatory variables (Stokes et al. 2012). The odds ratio, 95% confidence interval for the odds ratio, and p-value based on the fitted model will be reported. Confidence intervals for the percentages per treatment group will be presented and will be derived from the normal approximation to the

binomial distribution. Missing data will be imputed using “non-responder” (i.e., “negative” outcome) imputation.

Secondary efficacy variable 21 will be analyzed at each post-baseline visit using a proportional odds model with treatment and baseline LDL-C as explanatory variables (Stokes et al. 2012). The odds ratios, 95% confidence intervals for the odds ratios, and p-values based on the fitted model will be reported. Confidence intervals for the percentages per treatment group will be presented and will be derived from the normal approximation to the binomial distribution. Missing data will not be imputed.

Analyses of secondary efficacy variables will be based on the FAS.

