Participants who discontinue from study treatment should continue to attend the remaining study visits as indicated in the Assessment Schedule (Table 8-1).

Participants who discontinue from study or withdraw their consent should be scheduled for a final evaluation visit if they agree, as soon as possible, at which time all of the assessments listed for the final visit will be performed. At this final visit, all investigational product should be reconciled, and the adverse event and concomitant medications not previously reported must be recorded on the eCRF.

Participants will have to comply with the following restrictions during the study:

- Participants need to fast for at least 8 hours for all visits (measurement of lipids/lipoproteins and blood glucose requires participants to be fasting). If the participant has not fasted, the collection of laboratory evaluations must be rescheduled.
- Blood donation will not be allowed at any time during the study

The "X" in the table denotes the assessments to be recorded in the clinical database or received electronically from a vendor. The "S" in the table denotes the assessments that are only in the participant's source documentation and do not need to be recorded in the clinical database.

As per Section 4.6, during a Public Health emergency that limits or prevents on-site study visits, alternative methods of providing continuing care may be implemented by the investigator as the situation dictates. If allowable by a local Health Authority and depending on operational capabilities, phone calls, virtual contacts (e.g. tele consult) or visits by site staff/ home nursing staff to the participant's home, can replace on-site study visits, for the duration of the disruption until it is safe for the participant to visit the site again.

If a public health emergency limits or prevents on-site study visits, alternative methods of providing continuing care may be implemented. Virtual visits [e.g., phone calls, video visits (preferred)] or visits by site staff/home nursing service to the participant's home depending on local regulations and capabilities, can replace on-site study visits, for the duration of a public health emergency until it is safe for the participant to visit the site again.

Unscheduled Visits

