Data collected at scheduled or unscheduled visits will be used in the analysis if they fall into an analysis window for an analysis visit. If more than one visit (scheduled or unscheduled) is made within the window specified above for any analysis visit, the non-missing assessment closest to the target study day will be used in the analysis for that visit. In the case of tied visits, non-missing data from the later visit will be used. In the case of identical collection dates and times, the average of the two visits will be used. However, all data will be included in the participant data listings.

Last Visit Summaries

The protocol uses the term End of Study (EOS) for Day 330. If a participant discontinues from the study early, they will have an early termination visit that is before Day 330. Using the windowing provided in [Table 2-2](#), the early termination visit will be assigned to the nearest analysis visit. Tables that summarize data by visit will include data by analysis visit (Baseline, Day 90, Day 270, and Day 330) along with a Day 330/Last Visit which will combine data from Day 330 for those participants who have data collected within the Day 330 analysis window with the data from the last post-baseline visit for those participants who do not have data collected in the Day 330 analysis window.

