2.6.3 Handling of missing values

For the analysis of secondary efficacy variables 1 and 7-20, the MMRM implicitly imputes missing data under a missing at random assumption.

For the analysis of secondary efficacy variables 4 – 6 and 23, participants with missing data will be imputed using “non-responder” (i.e., “negative” outcome) imputation.

For the analysis of secondary efficacy variables 2, 3, 21 and 22, missing data will not be imputed.

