2.6.5 Supplementary analyses

Secondary efficacy variables 2 and 3 will be analyzed using MMRM similar to the analysis of primary efficacy variable 1 and secondary efficacy variable 1, respectively. A linear combination of the estimated means will be used to estimate the time-adjusted percent change and absolute change from baseline in LDL-C, where “time-adjusted” refers to the estimated average from Day 90 through Day 330. Least-squares mean of each treatment group, least-squares mean treatment difference, 95% confidence interval for the treatment difference, and p-value based on the fitted model will be reported.

Secondary efficacy variables 4 – 6 will be analyzed similar to the supplementary analysis of primary efficacy variable 2 based on observed data only.

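### The average LDL-C change (secondary variables 2 and 3) is taken over whichever visits each participant has, leaving it open to dropout bias that the SAP's own supplementary MMRM would reduce

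*SAP*

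**What the plan says.** SAP 2.6.2 sets the model: "Secondary efficacy variables 2, 3, and 22 will be analyzed using an analysis of covariance (ANCOVA) linear model". Its covariates are treatment and baseline LDL-C. It derives the outcome thus: "Variables 2 and 3 are calculated by averaging the observed post-baseline values (change or percent change) for each participant across analysis visits". The visits meant are those on Days 90, 270 and 330. There is no weight or model term for how many visits went into a participant's average. SAP 2.6.3 adds: "For the analysis of secondary efficacy variables 2, 3, 21 and 22, missing data will not be imputed".

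The same section treats the other continuous lipid variables differently: "For the analysis of secondary efficacy variables 1 and 7-20, the MMRM implicitly imputes missing data under a missing at random assumption".

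SAP 2.6.5 then lists a second analysis as supplementary: "Secondary efficacy variables 2 and 3 will be analyzed using MMRM similar to the analysis of primary efficacy variable 1", and similarly to secondary variable 1 for the absolute change. It uses a linear combination of the visit means, and its time-adjusted result "refers to the estimated average from Day 90 through Day 330". The weights are not given. SAP 2.6.4 plans no sensitivity analyses for the secondary variables.

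Two further rules decide who has incomplete data. Under SAP 2.1.1, "the early termination visit will be assigned to the nearest analysis visit", using the windows in Table 2-2: Days 1 to 180 count as Day 90, 181 to 300 as Day 270 and 301 to 375 as Day 330. Under Protocol Section 8, "Participants who discontinue from study treatment should continue to attend the remaining study visits as indicated in the Assessment Schedule".

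Protocol 12.5.1 names only a linear model for variables 2 and 3. It does not say how partial data enter the average.

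**The concern.** The quantity measured per participant changes with follow-up. Someone whose last LDL-C falls in the Day 1 to 180 window enters with that one value. Someone who leaves after the Day 270 visit enters with two. Both carry the same weight in the ANCOVA as a complete three-visit average, so the estimate tilts towards the earlier visits.

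That matters if the arms differ by a different amount early and late, and there are reasons to think they may. Protocol 4.1 puts maximum LDL-C reduction at about 4 to 5 months and says the second dose, given at Day 90, lowers LDL-C slightly further than the first. Doses fall on Days 0, 90 and 270, so Day 330 is 60 days after a dose, while Days 90 and 270 are themselves dosing visits. Usual care may be intensified at any time. None of this fixes the size or direction of a difference between visits.

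Outcome-related dropout is a second route. If participants who respond poorly at Day 90 leave more often in one arm, their poor Day 90 values stand for all three visits, although their later values would tend to lie closer to the arm mean.

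At stake are two secondary estimates of average LDL-C lowering over the study. No success criterion or sample-size target depends on them.

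**Working it through.** **The plan's own figure.** No sample size is given for variables 2 and 3. The nearest figure is for primary variable 1 (SAP Section 3: difference 15, SD 40, two-sided 0.025, power 0.85):

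n per arm = 2 × (2.2414 + 1.0364)² × 40² / 15² = 152.8, rounded up to 153, so 306 in total. Allowing for 20% loss, 153 / 0.8 = 191.25, rounded up to 192 per arm, so 384. Both match the plan. They supply the SD (40), the loss (20%) and the arm size (192) used below.

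**Assumptions.** The Day 90 and Day 270 effects, the timing and mechanism of dropout, and a within-person correlation of 0.6 are not in the documents. They are assumed and varied. Results are for percent change (variable 2); variable 3 was not sized.

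**Step 1: dropout unrelated to outcome, same pattern in both arms.** Let d90, d270 and d330 be the treatment differences, dbar their equal-weight mean, f1 the share with Day 90 only and f2 the share with Days 90 and 270.

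Bias = f1 × (d90 − dbar) + f2 × ((d90 + d270)/2 − dbar)

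Example: differences −10, −15, −15 give dbar = −13.33. If all 20% have Day 90 only, the estimate is 0.8 × (−13.33) + 0.2 × (−10) = −12.67, a bias of +0.67. Positive bias understates the benefit.

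| Differences at 90/270/330 | dbar | 20% Day 90 only | 10% and 10% | 20% lost after Day 270 |
|---|---|---|---|---|
| −15/−15/−15 | −15.00 | 0 | 0 | 0 |
| −12/−15/−15 | −14.00 | +0.40 | +0.25 | +0.10 |
| −10/−15/−15 | −13.33 | +0.67 | +0.42 | +0.17 |
| −20/−15/−15 | −16.67 | −0.67 | −0.42 | −0.17 |
| −15/−10/−20 | −15.00 | 0 | +0.25 | +0.50 |

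**Step 2: unequal loss, still unrelated to outcome.** Each arm now has its own bias, f1 × (its Day 90 mean − its three-visit mean). With inclisiran flat at −55, usual care at −35/−40/−40 (mean −38.33), and 10% versus 30% having Day 90 only: inclisiran 0; usual care 0.3 × (−35 + 38.33) = +1.00. The bias in the difference is −1.00.

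**Step 3: simulation.** 192 per arm, SD 40, 2,000 runs, all dropout after Day 90. The mechanism is either random or missing at random, with poor Day 90 responders leaving more often. Rates are nominal. The comparator is a likelihood-type estimator valid under missing at random, standing in for the MMRM. Baseline adjustment is left out. Monte Carlo error is about 3.6 / √2000 = 0.08.

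| Arm profiles at 90/270/330 | Dropout, inclisiran/usual care | Bias, observed-visit average | Bias, MMRM-type |
|---|---|---|---|
| −55 throughout; −40 throughout | MAR 20/20 | −0.11 | −0.13 |
| same | MAR 10/30 | −0.82 | +0.07 |
| −50/−55/−55; −40 throughout | MAR 20/20 | +0.69 | 0.00 |
| same | MAR 10/30 | −0.55 | 0.00 |
| −55 throughout; −35/−40/−40 | random 10/30 | −1.08 | −0.06 |
| same | MAR 10/30 | −1.82 | +0.03 |

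**Step 4: scale.** With complete data the SD of a three-visit mean is 40 × √((1 + 2 × 0.6)/3) = 34.25, so the standard error is 34.25 × √(2/192) = 3.50. The simulated standard errors were about 3.5 to 3.8 for both estimators. The largest bias is therefore about half a standard error (1.82 / 3.67 = 0.50), and the MMRM-type estimate costs no appreciable precision.

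**Step 5: unstated weights in SAP 2.6.5.** Take differences of 15, 10 and 20 at the three visits. Equal weights give (15 + 10 + 20)/3 = 15.0. Trapezoid time weights over Days 90 to 330 are 90/240, 120/240 and 30/240, giving 0.375 × 15 + 0.50 × 10 + 0.125 × 20 = 13.1. The present wording allows either.

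**The case against.** The strongest reply is that the matter is already covered. SAP 2.6.5 specifies the MMRM for exactly these two variables, with the difference, 95% interval and p-value, so both results will be reported. The default level is two-sided 0.05 and no testing hierarchy is stated for the secondary variables, so the choice is largely about which result is called the main one. The observed-visit ANCOVA also follows the protocol's linear model. All of that stands, and it is why this is a minor point. It does not explain why these two variables should have a main analysis more exposed to dropout than variables 1 and 7 to 20.

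Several stronger readings are tempting and are not supported:

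- A reader might infer that the result is certain to be biased in favour of inclisiran. With equal effects at all visits and uninformative dropout the bias is zero. If the Day 90 effect is the smaller one, which Protocol 4.1 makes plausible, equal loss understates the benefit.
- One can pick visit means that give a firm-looking overstatement. With −50/−48/−55 for inclisiran and −20/−35/−40 for usual care, the difference moves from −19.3 with full data to −20.6 (20% loss in each arm, half before and half after Day 270) or −21.1 (15% versus 25%), about 7 to 9%. Only the Day 330 means come from the plan. Protocol 4.1 also says that only a minority of eligible patients receive non-statin therapy, which argues against assuming strong intensification in usual care.
- A reader might assume that every early leaver contributes Day 90 alone. Those who leave after Day 270 contribute two visits, those who only stop study treatment should still attend, and those with no post-baseline sample contribute no outcome to either analysis.
- The term time-adjusted might suggest that time weights are required. The endpoint is an average over post-baseline visits, which equal weights match. Trapezoid weights would cut Day 330 from 1/3 to 1/8 and change what is estimated.

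**Conclusion.** The point holds as a low-priority refinement. The main analysis of variables 2 and 3 averages whatever visits were observed, imputes nothing and ignores the number of visits. A method valid under missing at random is already written for the same variables but ranked below it. The resulting bias is a risk, not an established fact. For percent change it ranged from 0 to about 1.8 percentage points in the scenarios examined, in either direction, against a standard error of about 3.6.

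The upper end needs usual care to improve after Day 90 together with outcome-related loss at nominal rates of 10% versus 30%, which average to the planned 20%. All sizes rest on assumed visit effects, dropout patterns and a correlation of 0.6. If dropout depends on unobserved LDL-C values, the MMRM is not protected either. The primary endpoints and the sample size are untouched.

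**What to change.** In SAP 2.6.2 and 2.6.3, make the MMRM linear combination of visit means from 2.6.5 the main analysis of variables 2 and 3, and state its weights. Weights of one third each for Days 90, 270 and 330 match the endpoint as defined. If a time-weighted average is wanted, give its weights and label it supplementary. Move the observed-visit ANCOVA to 2.6.5, and add a table by arm of participants contributing zero, one, two or three post-baseline visits.

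Both analyses are already specified, so the work is mainly wording. There is a small cost. The change departs from the linear model in Protocol 12.5.1, so it must be listed in SAP Section 4. Because the trial is open-label, it should be fixed before database lock. If the order of the two analyses is left as it is, the weights in 2.6.5 should still be stated, since two programmers could otherwise produce different results from the same text.
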